# 4.0 INVESTIGATIONAL PLAN

# 4.1 OVERALL STUDY DESIGN

This is a prospective, randomized, controlled, multi-center study that is intended to demonstrate that the frequency of hemostatic interventions/procedures required intraoperatively or post-operatively related to the transection of the renal artery (RA) and renal vein (RV) during simple, radical laparoscopic nephrectomies or laparoscopic nephroureterectomies with PVS is not increased when compared to standard of care (SOC).

Eligible subjects will be randomized pre procedure in a 1:1 ratio to either the surgeon's current SOC stapler or PVS. Subjects will be followed post-operatively through discharge and at 4 weeks post surgery (final visit can be conducted either by phone or office visit).

If the study surgeons have not completed previous ECHELON FLEX™ Powered Vascular Stapler with Advanced Placement Tip training, each surgeon must complete two procedures with ECHELON FLEX™ Powered Vascular Stapler with Advanced Placement Tip prior to their first randomized subject. These subjects will be considered part of a learning curve and will be analyzed separately from the randomized subjects.

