# 4.2.1 Inclusion Criteria

Subjects satisfying the following criteria will be eligible for participation in this study:

- 1. Scheduled for a simple or radical laparoscopic nephrectomy or a laparoscopic nephroureterectomy in accordance with the institution's standard of care (SOC);
- 2. Performance status 0-1 (Eastern Cooperative Oncology Group classification), if applicable;
- 3. ASA score < 3;
- 4. No prior history of partial or wedge nephrectomy (on the kidney in which the procedure will be performed);
- 5. Willing to give consent and comply with study-related evaluation and treatment schedule; and
- 6. At least 18 years of age.

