# 4.2.2 Exclusion Criteria

Subjects will be excluded from the study for any of the following:

- 1. Prior chemotherapy or radiation (within 30 days prior to the procedure or the duration of the subject's enrollment);
- 2. Pregnancy;
- 3. Physical or psychological condition which would impair study participation; or
- 4. The subject is judged unsuitable for study participation by the Investigator for any other reason

All subjects signing consent who do not meet the inclusion/exclusion criteria and therefore do not proceed to Visit 2/Procedure, and are not randomized, will be recorded as screen failures. The relevant electronic Case Report Form (eCRF) pages will be completed for all screen failure subjects and the data will therefore be included in the study database.

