# 4.4 REMOVAL OF SUBJECTS FROM STUDY

A subject has the right to withdraw from the study at any time for any reason without prejudice to his/her future medical care by the physician or the institution. Should a subject (or subject's legally authorized guardian/representative) decide to withdraw; all efforts will be made to collect and report the final visit observations as thoroughly and timely as possible.

Subjects who withdraw from the study prior to randomization will be considered screen failures and will be replaced. Subjects who withdraw from the study post-randomization, will not be replaced. Subject participation may be terminated prior to completing the study for any of the reasons listed below. When a subject's participation is terminated prior to completing the study, the reason for withdrawal is to be documented on the Study Completion eCRF as well as in the source documentation:

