#### Surgical:

The Investigator must withdraw a subject intraoperative for the following reasons:

- A simple or radical laparoscopic nephrectomy or laparoscopic nephroureterectomy not completed;
- Conversion to an open procedure, unless directly related to transection of the RA/RV (subject will be followed for safety up to 30 days postop); or
- Use of robotic assistance during surgery.

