Two-sided 95% Confidence Interval for Percent Difference (One-sided 95% CI Upper Limit) for Percent Requiring Transection [2]	xx.x%, xx.x%	xx.x%, xx.x%	xx.x%, xx.x%
	xx.x% (xx.x%)		
Type of Intervention, n (%) [3]			
Additional Stapling	xx (xx.x%)	xx (xx.x%)	xx (xx.x%)
Over-sewing	xx (xx.x%)	xx (xx.x%)	xx (xx.x%)
Compression	xx (xx.x%)	xx (xx.x%)	xx (xx.x%)
Use of Suture	xx (xx.x%)	xx (xx.x%)	xx (xx.x%)
Sealant	xx (xx.x%)	xx (xx.x%)	xx (xx.x%)
Buttress	xx (xx.x%)	xx (xx.x%)	xx (xx.x%)
Use of Energy	xx (xx.x%)	xx (xx.x%)	xx (xx.x%)
Clip Placement	xx (xx.x%)	xx (xx.x%)	xx (xx.x%)
Blood Product Transfusion	xx (xx.x%)	xx (xx.x%)	xx (xx.x%)
Additional Surgical Procedure	xx (xx.x%)	xx (xx.x%)	xx (xx.x%)
Other Intervention	xx (xx.x%)	xx (xx.x%)	xx (xx.x%)
Intervention Category, n (%) [4]			
No Intervention	xx (xx.x%)	xx (xx.x%)	xx (xx.x%)
Hemostasis Controllable	xx (xx.x%)	xx (xx.x%)	xx (xx.x%)
Hemostasis Intervention	xx (xx.x%)	xx (xx.x%)	xx (xx.x%)

[1] Denominator for calculation of percentage is the total number of vessels transected in that group.

[2] Difference is calculated as Powered Vascular Stapler minus Standard of Care Stapler.

[3] Denominator for calculation of percentage is the total number of vessels requiring intervention in that group.

[4] Hemostasis Controllable includes additional stapling, over-sewing, compression, use of suture, sealant, buttress, use of energy, clip placement, or other intervention.
 Hemostasis Intervention includes blood product transfusion and additional surgical procedure.

Table 7
 Post-Operative Interventions or Procedures Related to Renal Artery or Renal Vein Bleeding
 Safety Set

Characteristics	Standard of Care Stapler (N = ##)	Powered Vascular Stapler (N = ##)	Overall (N = ##)
Number of Subjects Requiring Post-Operative Intervention Related to Renal Artery or Renal Vein Bleeding			
n (%) [1]	xx (xx.x%)	xx (xx.x%)	xx (xx.x%)
95% Confidence Interval for Percent	xx.x%, xx.x%	xx.x%, xx.x%	xx.x%, xx.x%
Type of Intervention, n (%) [2]			
Blood Product Transfusion	xx (xx.x%)	xx (xx.x%)	xx (xx.x%)
Additional Surgical Procedure	xx (xx.x%)	xx (xx.x%)	xx (xx.x%)
Other Intervention	xx (xx.x%)	xx (xx.x%)	xx (xx.x%)

[1] Denominator for calculation of percentage is the total number of subjects in that group.
 [2] Denominator for calculation of percentage is the total number of subjects requiring intervention in that group.

Table 8
 Device Usage Details
 Full Analysis Set

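### Planned robotic assistance is not screened for before randomisation but forces withdrawal during surgery, and these subjects stay in the primary safety denominator with no stated follow-up

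*Protocol*

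**What the plan says.** **Eligibility.** Inclusion 1 (Protocol 4.2.1 and Synopsis) requires a subject to be "Scheduled for a simple or radical laparoscopic nephrectomy or a laparoscopic nephroureterectomy in accordance with" the institution's standard of care. None of the four exclusions in 4.2.2 mentions robotics. The only one that could be stretched to it is a matter of judgement: "The subject is judged unsuitable for study participation by the Investigator for any other reason".

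**Withdrawal.** Section 4.4, under Surgical, is not discretionary: "The Investigator must withdraw a subject intraoperative for the following reasons". The third reason listed is "Use of robotic assistance during surgery".

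**Replacement.** Section 4.4 also says: "Subjects who withdraw from the study post-randomization, will not be replaced". Subjects who leave before randomisation are screen failures and are replaced.

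**Timing.** Protocol 4.1 says "Eligible subjects will be randomized pre procedure in a 1:1 ratio", and 4.7.3.1 lists randomisation among the items to be completed before surgery. SAP section 3 allows it at any point before surgery and as late as vessel transection. It adds that sites were told to leave it as late as they could, to limit drops after randomisation.

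**Follow-up.** In the Surgical list of 4.4, safety follow-up (up to 30 days) appears only in the bullet on conversion to open surgery. The commitment in 4.4 to obtain final-visit observations is written for subjects who themselves decide to withdraw. Section 9.2.1 ends adverse event recording at study completion or early termination.

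**Analysis.** The Safety Set is every randomised subject whose procedure was started (Protocol 7.3, SAP section 7). SAP 10.4 analyses the primary safety endpoint from one record and one event indicator per subject. The first footnote to SAP Table 7 reads "Denominator for calculation of percentage is the total number of subjects in that group". Protocol 7.5.1 and SAP 10.6 restrict summaries to observed data, without imputation.

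**The concern.** Planned use of a robot is normally known when the operation is booked, yet the plan acts on it only after randomisation, when a lost subject can no longer be replaced. That is an avoidable post-randomisation exclusion.

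The greater stake is the primary safety endpoint: transfusion or further surgery for post-operative bleeding, ascertained through discharge and at the 4-week visit. A subject withdrawn in the operating room may have no Visit 3 or Visit 4 data but still counts in the Safety Set. If the event indicator defaults to no event, the reported rate is too low for a reason unrelated to either stapler.

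**Working it through.** The point is mainly textual. The one planned figure it could touch is the per-arm margin of error, so that is checked first.

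**1. The plan's precision figure.** Inputs (Protocol 7.2, SAP section 8): intervention rate 6%, at least 300 firings per arm, margin at most 2.9%.
- Wald half-width: 1.96 × √(0.06 × 0.94 / 300) = 2.69%.
- Clopper-Pearson with 18 of 300: 3.59% to 9.32%, half-width 2.86%.

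The stated figure is reproduced.

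**2. Would robotic withdrawals move it?** The documents give no robotic share, so 5% and 10% are assumptions, as is the loss of all firings from those subjects. With 125 subjects per arm, 300 firings means 300 / 125 = 2.4 per subject.
- 5% lost: 118.75 × 2.4 = 285 firings; half-width 2.94% exact, 2.76% Wald.
- 10% lost: 112.5 × 2.4 = 270 firings; half-width 3.03% exact, 2.83% Wald.

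The exact margin just passes 2.9% and the Wald margin does not. The plan's own range of 2 to 3 firings per subject matters more:
- At 2 per subject, 125 × 2 = 250 firings with no loss at all (exact 3.15%, Wald 2.94%).
- At 3 per subject, a 20% loss still leaves 100 × 3 = 300.

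**3. The route to withdrawal, with the sections side by side.**
- A subject booked for robot-assisted laparoscopic surgery at a site where that is standard can satisfy 4.2.1, and meets no named exclusion in 4.2.2.
- Under 4.1 and 4.7.3.1 the subject is randomised before surgery.
- Once the robot is used, 4.4 requires withdrawal.
- Under 4.4 the subject is not replaced. That sentence speaks of subjects who withdraw; applying it to withdrawal by the investigator is the natural reading, since both stand in the same section.

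For scale only: if 2% to 10% of randomised subjects took this route, that is 250 × 0.02 = 5 to 250 × 0.10 = 25 subjects.

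**4. The safety denominator.** Let N be the Safety Set in one arm, u the fraction withdrawn and not followed, and p the true risk, assumed equal in followed and unfollowed subjects. If unfollowed subjects are scored as event-free, the expected Table 7 proportion is

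p × N(1 − u) / N = p(1 − u),

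so the relative understatement is u. If u is 2%, 5% or 10%, the rate is understated by 2%, 5% or 10% of itself. The plan states no expected post-operative rate, so no absolute figure follows.

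If only followed subjects were counted, the denominator would be N(1 − u) and this bias would vanish under the same assumption. The SAP does not choose: its missing-data rule points to the second reading and the Table 7 footnote to the first.

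**The case against.** The best reply is SAP section 3. If sites opened the envelope close to transection, a robotic case would usually be recognised first and would become a replaceable screen failure. This stands as a reason to expect few cases. It does not close the gap: the same section allows randomisation at any earlier time, the Protocol places it before the procedure, and neither mentions robotics.

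A second reply is that laparoscopic surgery means non-robotic surgery, or that the investigator can use exclusion 4. The first is a possible reading that the documents never state. The second sets a discretionary screen against a mandatory withdrawal.

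Third, the follow-up gap is not peculiar to robotics, because the bullet on procedures not completed has it too. That is true, and the remedy can cover both.

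A reader might also infer more than the documents support:
- *Withdrawn subjects are lost to the primary performance analysis.* Not necessarily. The Full Analysis Set needs a performed procedure and intervention data, and nothing in it removes a subject for withdrawal. The endpoint is intra-operative, so firing data may exist.
- *Robotic losses push firings below 300.* Whether 300 is reached depends mainly on firings per subject, as step 2 shows.
- *The loss differs by arm because surgeons know the allocation.* The study is open-label, but nothing in the documents links stapler allocation to robot use.
- *The safety rate is certainly understated.* The no-imputation rule argues against scoring unfollowed subjects as event-free. The footnote leaves that open; it does not establish the error.

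**Conclusion.** The point holds in limited form. Eligibility and section 4.4 do not fit together: planned robotic use is not screened for, forces withdrawal after randomisation, and costs a subject who is not replaced. Late randomisation lowers the frequency without removing the problem. Any loss of precision is secondary and occurs only if firing data from these subjects go unused.

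The consequence that matters is in the primary safety endpoint, where subjects with no stated post-operative follow-up stay in the Safety Set and, by the footnote, in the Table 7 denominator. The direction is understatement, on condition that they are unfollowed and counted as event-free. The amount cannot be derived from the documents; the 2% to 10% shares are illustrations, and the proportional result assumes equal risk in followed and unfollowed subjects. The change is nearly free and protects a primary endpoint, so it should be made.

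**What to change.** **Protocol.**
- Reconcile 4.2.1, 4.2.2 and the Synopsis with 4.4 by adding a check for planned robotic assistance at Visit 1, repeated at Visit 2 before randomisation. Such cases then become screen failures.
- In 4.4, state that a subject withdrawn after randomisation for robotic use still contributes Visit 3 and Visit 4 data for the primary safety endpoint, unless consent is withdrawn. The same sentence can cover procedures not completed.

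**SAP.**
- Section 7: state that randomised robotic cases with RA/RV firing data stay in the Full Analysis Set, as its definition already allows, and that robotic use is handled as a deviation when the Per Protocol set is formed.
- Table 7: base the denominator on subjects with observed post-operative follow-up, or keep all Safety Set subjects and report the number unfollowed by arm.
- Table 1: split the single Surgical row so that robotic withdrawals are visible by arm.

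The cost is a few more screen failures at sites that use robots, a few follow-up contacts, and some robot-assisted cases in the Full Analysis Set. The SAP is written largely in the past tense. If enrolment has closed, the eligibility check comes too late, but the SAP changes can still be made.

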#### Adverse Event:

• When the subject experiences an adverse event and the Principal Investigator or Medical Director believes it is in their best interest to discontinue participation in the study, they will be withdrawn.

#### Death:

When possible, the cause of death will be documented.

#### Lost to follow-up:

When contact with the subject has been lost without completing a final visit assessment, and every attempt to contact has failed, the subject will be considered lost to follow-up. Final

documentation regarding all attempts to contact the subject requesting their return for the final visit should be documented.

#### Site Termination or Study Termination:

A site or study may be terminated. When this occurs all subjects at the site will be withdrawn and documented as early termination. Reasons for site or study termination may include, but are not limited to the following:

- Administrative Concerns (e.g., inadequate subject enrollment, investigator/institution non-compliance, change of business strategy, etc.);
- Safety Issues, including those due to non-compliance, which substantially affect the risk to benefit ratio of the study subjects at a site or for the study as a whole; and
- Regulatory Body Mandate(s).

The Investigator has the right to terminate their participation at any time. Should this be necessary, procedures for termination will be provided by the Sponsor.

# 4.5 IDENTITY OF STUDY PRODUCT(S)

Product Code	Product Name	Manufacturer
PVE35A	ECHELON FLEX™ Powered Vascular Stapler with Advanced Placement Tip	Ethicon Endo-Surgery, LLC (Guaynabo, Puerto Rico, USA)
VASECR35	ENDOPATH ECHELON Vascular White Reload for Advanced Placement Tip	Ethicon Endo-Surgery, LLC (Guaynabo, Puerto Rico, USA)

The ECHELON FLEX™ Powered Vascular Stapler with Advanced Placement Tip is a sterile, single use instrument that simultaneously cuts and staples tissue. There are four staggered rows of staples, two on either side of the cut line. The ECHELON FLEX™ Powered Vascular Stapler with Advanced Placement Tip and reloads have a staple line that is approximately 35mm long and a cut line that is approximately 30 mm long. The shaft can rotate freely in both directions and an articulation mechanism enables the distal portion of the shaft to pivot to facilitate lateral access to the operative site.

Powered vascular stapler has been cleared for marketing by the FDA and is CE marked which allows for commercial distribution in the EU. The device will be used in accordance with product labeling and Instructions for Use (IFU).

# 4.6 PRODUCT ACCOUNTABILITY

The ECHELON FLEX™ Powered Vascular Stapler with Advanced Placement Tip and cartridges will be provided by the Sponsor and will be tracked using shipping invoices and device accountability logs. All product returns will be managed by contacting the Sponsor.

The powered vascular staplers must be kept in a secure area. Devices will only be used for treating subjects participating in the study, in accordance with the protocol. The study device inventory must be available for periodic inspection/verification.

# 4.7 STUDY PROCEDURES

# **4.7.1 Procedure Description**

A simple or radical laparoscopic nephrectomy or a laparoscopic nephroureterectomy will be performed according to the institution's SOC.

# 4.7.2 Visit 1 – Screening (can occur over several dates within 1-2 weeks of Visit 2- Procedure)

Subjects will be evaluated according to the local investigator's preferred practice. Subjects will be selected for a surgical procedure based on the preoperative investigations and the local investigator's interpretation of the clinical picture.

Eligible subjects will be provided with the study information including the ICD.

The following screening activities will occur prior to the study procedure:

- The subject must be given ample time to review and sign the ICD;
- Collection of demographic information (year of birth, gender, ethnicity);
- Review and collection of relevant medical/surgical history, history of hypertension if applicable;
- Review/collection of inclusion/exclusion criteria and determination as to whether the subject is eligible for participation (retrospective data, per site SOC, is permitted to determine eligibility); and
- Anticoagulants taken preoperatively (up to 30 days prior to Visit 2), including stop date

# 4.7.3 Visit 2 – Procedure

# 4.7.3.1 Pre-procedure

The following must be obtained prior to the surgical procedure:

- Date of hospital admission;
- Update to medical / surgical history, if applicable;
- Confirm inclusion and exclusion criteria;
- ASA score; and
- Randomization

# 4.7.3.2 Intraoperative

Data collected during procedure:

• Overall Operating Room (OR) time ;

- Duration of procedure (first incision to skin closure);
  - Includes time to completion of resection (capturing the time laparoscopic camera is inserted until the specimen is received)
- Procedure data:
  - Type of surgery;
  - Number of renal arteries (1, 2, or 3+);
  - Location of affected kidney;
  - Confirm visualization of the cut line indicator field prior to transection;
  - Number of ports;
  - Intraoperative surgical interventions (not associated with transection of the RA/RV), if applicable;
  - Number and type of drain tubes placed, if applicable;
  - Reason for conversion to open surgery, if applicable;
  - Volume of estimated intra-operative blood loss;
  - Transfusion products (and rationale for use), if applicable;
  - Concomitant procedures/interventions performed, if applicable;
  - Tumor size and TNM staging, if available or applicable
- Intra-operative interventions/procedures on RA/RV to stop bleeding, if applicable;
  - Hemostasis intervention: bleeding detected and controlled intraoperatively (additional stapling, over-sewing, clip placement, compression, use of suture, sealant, and/or buttress, and/or use of energy); or bleeding that occurs intra-operatively requiring blood or blood product transfusion or an additional surgical procedure (e.g. conversion to open).
- Device usage data:
  - Usability and articulation questions;
- Surgeon Device Questionnaire (*PVS procedures only*);
- Surgeon Satisfaction Questionnaire (SOC and PVS procedures);
- SURG-TLX (SOC and PVS procedures);
- Adverse Events; and
- Concomitant medication (associated with AEs)

# 4.7.4 Visit 3 – Postoperative through Discharge

Post procedure assessments will be completed from OR discharge until hospital discharge. Data to be collected includes:

• Post-operative interventions/procedures related to RA/RV bleeding, if applicable:

- Hemostasis intervention: bleeding that occurs post-operatively requiring blood or blood product transfusion or an additional surgical procedure (and the relationship to SOC/PVS for RA/RV transection);
- Date of drain removal, if applicable
- Daily volume and characteristics of drainage (drain);
- Concomitant procedures/ interventions performed, if applicable;
- Adverse Events;
- Concomitant medication (associated with AEs); and
- Discharge date

# 4.7.5 Visit 4-Final Visit (4 week follow up, post procedure)

This visit can be either an office visit or a telephone followup visit. Data to be collected includes:

- Post-operative interventions/procedures related to RA/RV bleeding, if applicable:
  - Hemostasis intervention: Bleeding that occurs post-operatively requiring blood or blood product transfusion or an additional surgical procedure (and the relationship to SOC/PVS for RA/RV transection);
  - Concomitant procedures/interventions performed, if applicable;
  - Date of drain removal, if applicable
  - Daily volume and characteristics of drainage (drain), if applicable;
  - Adverse Events;
  - Concomitant medication (associated with AEs); and
  - Subject exited from the study

# 5.0 DATA MANAGEMENT AND INTEGRITY

# 5.1 DATA COMPLETION AND RECORD KEEPING

# 5.1.1 Source Documents

Source documents are documents on which information regarding subjects is first recorded, including printed, hand written, or electronic documents. Investigator subject files or hospital records generally are the basis of source document information. This includes but is not limited to, original subject files; hospital/clinic records; original recordings /tracing; digital images from automated instruments (e.g., cameras); radiographs; device accountability records; photographic negatives; and records kept at the investigation site, at the laboratories and at other departments involved in the clinical investigation.

Source documents must be retained by the Investigator as part of the subject's permanent medical record. The information in the source documents is used to complete the eCRFs. All information captured on the eCRFs should be completely and accurately supported in source documentation. Any additional

information relevant to the study should be included in the source documents. The Investigator will retain originals of all source documents, subject consent forms, and study data.

